**Visit 2/week 2 (between 2 weeks and 4 weeks):**

- We will apply ultrasound gel and measure inter-rectus distance (IRD), 2 cm above and 2 cm below the umbilical ring, via ultrasound or palpation with tape measure (measurement will be same technique as original measurement)

**Visit 3/week 4-12 (between week 4 and 12):**

- We will apply ultrasound gel and measure inter-rectus distance (IRD), 2 cm above and 2 cm below the umbilical ring, via ultrasound or palpation with tape measure (measurement will be same technique as original measurement)

-Administer Body Image States Scale (BISS) (5 minutes)

-Administer Pelvic Floor Impact Questionnaire- short form 7 (PFIQ-7) (5 minutes)

-Obtain Defense and Veterans Pain Rating Scale for lumbar pain and pelvic pain (DVPRS) (5 minutes)

Microcurrent Device: We will be using the Inspirstar microcurrent stimulator TENS device. It is an FDA 510k approved portable hand-held device used for the symptomatic relief of chronic pain. It generates low current intensity pulses in the ranges of 20 $\mu$ A to 400 $\mu$ A. For this study, we will use a treatment range of 100-300 $\mu$ A.

**10.2 Data Collection:**

Describe all the data variables, information to be collected, the source of the data, and how the data will be operationally measured.

-Variables: Age, parity, pregnancy weight-gain (from medical record), BMI

-Information to be collected: Demographics (age, weight, height, BMI, parity, medical and pregnancy history, assessments (pain, body image, strength, urogynecologic symptoms)

-Source of data: Patient

**10.3 At any point in the study, will you request, use, or access health information in any form, including verbal, hard copy and electronic?**

Yes  No

**11.0****Statistical/Data Analysis Plan****11.1 Statistical Considerations:**

List the statistical methods to be used to address the primary and secondary objectives, specific aims, and/or research hypotheses. Explain how missing data and outliers will be handled in the analysis. The analysis plan should be consistent with the study objectives. Include any sub-group analyses (e.g., gender or age group). Specify statistical methods and variables for each analysis. Describe how confounding variables will be controlled in the data analysis

The primary outcome measures are inter-rectus distances (IRD) taken 2 cm above and 2 cm below the umbilical ring. Secondary outcome measures taken once at the final postpartum visit between weeks 4 and 12 are Body Image States Scale (BISS); Pelvic Floor Impact Questionnaire- short form 7 (PFIQ-7); and Defense and Veterans Pain Rating Scale for lumbar pain and pelvic pain (DVPRS). Employing these outcome measures, the statistical null hypotheses are as follows:

- H01 — there are no differences in IRD means between times, locations and treatment groups
- H02 — there are no differences in BISS means between treatment groups
- H03 — there are no differences in PFIQ-7 means between treatment groups
- H04 — there are no differences in DVPRS means between treatment groups

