**Screening visit (within 3 months postpartum):**

- Obtain and document signed Informed Consent and HIPAA authorization.
- Review past medical and pregnancy history to verify inclusion and exclusion criteria.
- Collect demographic information to include age, weight (pounds), height (inches), BMI, DoD ID#, current email address (for scheduling), phone number, race, ethnicity.

**Randomization:** Subjects will be randomized into one of two research treatment groups with approximately 58 subjects in each arm:

- Group 1: Sham (fake) microcurrent therapy (placing the microcurrent pads on the patient and turning the microcurrent box on placebo mode ), for one treatment lasting a total of 7 hours and 10 minutes the device will worn at home and returned.
- Group 2: Frequency specific microcurrent therapy (100-300 $\mu$ A microcurrent amps) with Diastasis Recti Repair protocol (8), for one treatment lasting a total of 7 hours and 10 minutes the device will be worn at home and returned.

**Blinding:** [name] will be responsible for managing the excel spreadsheet that randomly assigns the patient to Group 1 or Group 2. She will place the randomization code into a sealed envelope and deliver it to the Research Technicians who will program the microcurrent boxes to either Group 1 (Sham microcurrent therapy) or Group 2 (microcurrent therapy). The blinded microcurrent boxes will be provided to the study staff to apply the microcurrent treatment. The remaining study staff will be blinded to the study treatment. If at any time a patient experiences an adverse event that requires breaking of the blind, [name] can provide the randomization assignment. At the conclusion of the study, and once all the subjects have completed treatment and follow up, [name] will provide the randomization assignments to the study staff to be included in the data analysis.

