**Visit 1 (may be the same day as screening visit):**

- We will apply ultrasound gel and measure inter-rectus distance (IRD), 2 cm above and 2 cm below the umbilical ring, via ultrasound or if unable via ultrasound, via palpation and measuring tape.

-Begin treatment according to randomization group, patients will be instructed to leave microcurrent in place until treatment is over. Subjects will return to the clinic the day after visit 1 so that Research personnel can retrieve the microcurrent box. We will apply ultrasound gel and measure inter-rectus distance (IRD), 2 cm above and 2 cm below the umbilical ring, via ultrasound or palpation with tape measure (measurement will be the same technique as the original measurement).

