#### **14.4**

#### **Potential Benefits:**

Describe any real and potential benefits of the research to the subject and any potential benefits to a specific community or society

If the individuals in the research are considered experimental subjects (per 10 USC 980), and they cannot provide their own consent, the protocol must describe the intent to directly benefit all subjects

Subjects may experience an improvement in diastasis rectus abdominus (DRA), improvement in abdominal wall functionality, reduction of pain, improvement in body image, improvement in urogynecologic symptoms; however, this is not a guarantee.

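### BISS and PFIQ-7 have no pre-treatment score, so H02 and H03 are valid against sham but lose precision, and change from baseline cannot be estimated

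*Combined protocol and SAP*

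**What the plan says.** Section 11.1 introduces the three questionnaires as "Secondary outcome measures taken once at the final postpartum visit between weeks 4 and 12". The visit schedule in section 10.1 agrees: "Administer Body Image States Scale (BISS) (5 minutes" and "Administer Pelvic Floor Impact Questionnaire- short form 7 (PFIQ-7) (5 minutes", each put at five minutes, appear under Visit 3 only.

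Nothing earlier in the schedule supplies a baseline:

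- Screening covers consent, medical and pregnancy history, and demographics ("Collect demographic information to include age, weight (pounds), height (inches), BMI" and similar items).
- The pre-treatment measurement at Visit 1 is IRD alone: "We will apply ultrasound gel and measure inter-rectus distance (IRD), 2 cm above and 2 cm below the umbilical ring".
- Visit 2 is also IRD alone.
- Section 10.2 names "assessments (pain, body image, strength, urogynecologic symptoms" among the information to be collected, but ties none of it to a visit.

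The hypotheses concern group means. H02 reads "there are no differences in BISS means between treatment groups", and H03 has the same form for PFIQ-7. Section 11.6 tests H02 to H04 by two-sample t-test or Mann-Whitney U, depending on normality, with no covariate. The sample size in section 11.5 is justified for IRD only.

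**The concern.** Where a questionnaire score after treatment is correlated with the same woman's score before treatment, part of the spread in final scores was already there at entry. A comparison of final scores alone leaves that part in the error term. A pre-treatment score used as a covariate removes it.

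Three things are at stake. First, H02 and H03 are tested with less precision than the same women could give, in a trial not sized for them. Second, if the arms happen to differ at entry on body image or pelvic symptoms, nobody can see it or adjust for it. Third, change within a woman cannot be estimated, although section 14.4 mentions "improvement in body image, improvement in urogynecologic symptoms" as possible benefits. A baseline not taken before the device is started cannot be recovered later.

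**Working it through.** **Inputs from the documents.** Planned completers 98 (section 11.2), taken as 49 per arm under the equal allocation of sections 10.1 and 11.4. Planned enrolment 116. Alpha 0.05 (section 11.5), used two-sided here.

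**Input not in the documents.** The correlation *r* between a pre-treatment and a Visit 3 score. I assume 0.3, 0.5 and 0.7 to show a range.

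**Step 1: the plan's own power figure.** Section 11.5 states 0.801 for IRD with 98 subjects and 3 repeated measures. Take the smallest standardised effect there, 0.36/0.77 = 0.468, so f = 0.468/2 = 0.234. Use the between-groups repeated-measures F-test with an assumed correlation of 0.5 between repeats:

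λ = f² × N × m / (1 + (m − 1)ρ) = 0.234² × 98 × 3 / (1 + 2 × 0.5) = 8.03, with df 1 and 96.

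Power is 0.801, which matches the plan. The 98 is therefore a number derived for IRD; no power is stated for BISS or PFIQ-7.

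**Step 2: the H02/H03 test as planned.** For a two-sample t-test with n = 49 per arm and df = 96, the noncentrality is d × √(n/2). Solving for 80% power gives d = 0.572 SD. At a true difference of 0.5 SD the noncentrality is 0.5 × √24.5 = 2.47 and power is 0.688.

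**Step 3: the same test adjusted for a baseline score.** ANCOVA multiplies the residual SD by √(1 − r²). The detectable difference becomes 0.572 × √(1 − r²), power at 0.5 SD is that of a standardised effect 0.5/√(1 − r²), and the equivalent sample-size multiple is 1/(1 − r²).

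| r (assumed) | √(1 − r²) | Detectable at 80% power (SD) | Power at 0.5 SD | Sample-size multiple |
|---|---|---|---|---|
| none (as planned) | 1 | 0.572 | 0.688 | 1 |
| 0.3 | 0.954 | 0.545 | 0.729 | 1.10 |
| 0.5 | 0.866 | 0.495 | 0.808 | 1.33 |
| 0.7 | 0.714 | 0.408 | 0.929 | 1.96 |

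These figures assume normally distributed scores. They do not describe the Mann-Whitney route.

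**Step 4: chance imbalance at entry.** With 49 per arm, the baseline difference between arms has a 95% range of ±1.96 × √(2/49) = ±0.40 SD. The part carried into the final difference is r times that: ±0.12 SD at 0.3, ±0.20 SD at 0.5, ±0.28 SD at 0.7.

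**Step 5: is the planned test still valid?** In 20,000 simulated null trials at each of r = 0.5 and 0.7, the unadjusted test of final scores rejected in 5.0% of trials, with a mean difference of about zero. The imbalance in Step 4 is already in the standard error of the t-test. It widens the interval and does not bias the estimate.

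**The case against.** The strongest reply is that nothing here is invalid. Section 9.4 describes a randomised, double-blind comparison with sham, so a difference in final scores estimates the treatment effect without bias. H02 and H03 ask only for a difference in means between groups, and section 9.2 sets the secondary aim as assessing these domains after therapy. None of these promises change from baseline. All of that stands.

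It rules out two stronger readings. A reader might infer that improvement cannot be shown at all. The documents do not support this: better scores than sham can be shown, and only within-woman change cannot. The word appears for these domains in the potential-benefits text of section 14.4, which is hedged there and is neither a hypothesis nor an endpoint. A reader might also infer that a positive or null result could not be told apart from a difference already present at entry. That fails too, because the test allows for chance imbalance, as Step 5 shows.

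The size of the gain is also open. The documents give no correlation, and a low one cannot be excluded: women may enter at any time up to 3 months postpartum and Visit 3 spans weeks 4 to 12. At 0.3 the detectable difference falls only from 0.57 to 0.55 SD. Finally, these are secondary outcomes that the trial was not sized for.

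These points limit the weight of the concern. They do not give a reason to leave out a cheap baseline.

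**Conclusion.** The point holds as one of efficiency and interpretability. BISS and PFIQ-7 are measured only at Visit 3 and tested without adjustment. The comparison with sham is valid and unbiased, but less precise than it could be; chance imbalance can be neither seen nor adjusted for; and change from baseline cannot be estimated.

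The gain from a baseline runs from small (equivalent to 1.10 times the sample at an assumed correlation of 0.3) to large (1.96 times at 0.7). It rests on 49 completers per arm, approximately normal scores, and correlations that the documents do not supply. The change is worth making because it costs little and cannot be made later for women already treated. It is not a condition for the trial's validity.

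**What to change.** Give BISS and PFIQ-7 at Visit 1, before the device is started. DVPRS has the same timing and can be covered by the same addition.

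Test H02 and H03 by ANCOVA of the Visit 3 score on arm and Visit 1 score, reporting the adjusted difference with a 95% CI. If residuals are clearly non-normal, use a rank-based ANCOVA in place of the Mann-Whitney test, so that the baseline is still used. Do not substitute raw change scores: their variance is 2(1 − r) times that of the final score, so they are noisier than final scores when r is below 0.5.

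Three places need amending: section 10.1 (Visit 1), section 11.1 (which says these measures are taken once, at the final visit) and section 11.6 (the tests).

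The cost is about 10 minutes of forms per woman at a visit she already attends, or 15 if DVPRS is included, using the same instruments and no new staff. A further benefit is that the 116 − 98 = 18 women not expected to complete would have a pre-treatment score, so completers and non-completers could be compared. If a baseline cannot be added, confine the reported conclusions to between-group differences at the final visit.

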## 11.2 Sample Size:

Planned to Enroll: 116  
Planned to Complete: 98

## 11.3 Total number of subjects requested (including records and specimens):

116

## 11.4 If you are recruiting by study arm, please identify the arms of the study and how many subjects will be enrolled in each arm

Randomization: Subjects will be randomized into one of two research treatment groups with approximately 58 subjects in each arm:

-Group 1: Sham (fake) microcurrent therapy (placing the microcurrent pads on the patient and turning the microcurrent box on placebo mode ), for one treatment lasting a total of 7 hours and 10 minutes the device will be worn at home and returned. Group 2: Frequency specific microcurrent therapy (100-300 $\mu$ A microcurrent amps) with Diastasis Recti Repair protocol (8), for one treatment lasting a total of 7 hours and 10 minutes the device will be worn at home and returned.

## 11.5 Please provide a justification for your sample size

Subjects will be a random sample of patients meeting the inclusion criteria. Subjects are presumed to be a random representation of the population of patients obtaining similar care at this and other Air Force medical treatment facilities. The main treatment effect is treatment using microcurrent electrical neuromuscular stimulation. Group 1 will receive a placebo effect and Group 2 will receive the treatment effect.

The study is organized as a mixed effects, randomized complete block design with repeated measures. Subject is a random effect as subjects will have been randomly subject to DRA from the population of patients obtaining similar care at these Air Force medical treatment facilities, randomly enrolled from this population of patients, and randomly assigned to treatment groups at the time of enrollment. Fixed effects are treatment group, time of repeated measure, and IRD location as these effects cannot be generalized to other treatments, times or locations.

A priori power was assessed using G\*Power Version 3.1.9.3. (9) The researchers wish to detect at least a 30% difference in IRD between the treatment groups. The mean (SD) IRD at the four locations at 7 weeks postpartum has been estimated to be 1.97 (0.71) cm, 2.39 (0.59) cm, 1.99 (0.65) cm, and 1.30 (0.77) cm respectively, and the minimally detectable changes at a 95% confidence level to be 0.45 cm, 0.47 cm, 0.55 cm and 0.36 cm respectively. (10) These are smaller differences, but near the stated research objective; therefore, these will be used as a conservative effect size to estimate a priori power. The results indicate 98 subjects with 3 repeated measures will have a power of 0.801 at  $\alpha = 0.05$  to detect these minimally detectable differences between the treatment groups.

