## 11.6 Data Analysis Plan: Complete description: Background, Objectives, Design, Step by Step how the project is going to be done, Data analysis plan:

Means, standard deviations, medians, interquartile ranges (IQR) and ranges will be calculated for interval variables. These variables include patient characteristics and physiological measurements such as age, weight, height, BMI, and pregnancy weight gain. Frequency distributions will be calculated for nominal variables that include race/ethnicity, and parity.

Null hypothesis H01 will be tested by a mixed effects repeated measures analysis of variance (rANOVA) controlling for location and treatment group. In the event the null hypothesis is rejected, contrasts will be used to investigate sub-group differences. The significance level of multiple comparison tests will be corrected to  $\alpha = .05$  by the Holm method. (11) Null hypotheses H02 to H04 will be tested with a two sample t-test or Mann-Whitney U test depending on whether the data is distributed normally or non-normally.

[name], Senior Research Biostatistician Subject Matter Expert for Clinical Research Management under contracts OMNI 0004 3-82 and OMNI 0005 3-126, is the statistical consultant supporting this study. Statistical analysis will be performed with R Version 3.5.1. (12)

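### Sections 11.5 and 11.6 name only subject as a random effect and state no error strata or covariance; fitted as listed, the IRD model can mis-size its time, location and change contrasts in either direction

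*Combined protocol and SAP*

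**What the plan says.** Section 11.1 sets the endpoint: "The primary outcome measures are inter-rectus distances (IRD) taken 2 cm above and 2 cm below the umbilical ring". Its null hypothesis H01 is that "there are no differences in IRD means between times, locations and treatment groups".

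Section 11.5 describes the design: "The study is organized as a mixed effects, randomized complete block design with repeated measures". It then sorts the factors: "Subject is a random effect as subjects will have been randomly subject to DRA", and "Fixed effects are treatment group, time of repeated measure, and IRD location".

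Section 11.6 names the test: "Null hypothesis H01 will be tested by a mixed effects repeated measures analysis of variance (rANOVA) controlling for location and treatment group". If H01 is rejected, contrasts follow, with Holm correction.

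No interaction is named. There are no error strata, covariance structure, sphericity correction or degrees-of-freedom method.

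Section 10.1 gives the measurement schedule. IRD is read at Visit 1 before treatment and again the next day ("Subjects will return to the clinic the day after visit 1 so that Research personnel can retrieve the microcurrent box"). It is read again between weeks 2 and 4, and between weeks 4 and 12. That is two locations on four occasions, or eight readings per woman.

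**The concern.** Two readings taken at the same visit share whatever moved that woman's IRD that day. Readings at the same location share that location's anatomy. A subject intercept alone carries neither, and it also assumes equal correlation between all occasions. Here the gaps run from one day to several weeks, and the last window is eight weeks wide, so equal correlation is hard to believe.

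The first reading precedes treatment, so a benefit would appear as a group difference in change from baseline. Those are the comparisons a mis-specified within-subject error damages. The follow-up contrasts in 11.6 would inherit the same error term, and Holm correction does not repair a wrong standard error.

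**Working it through.** **The plan's own figure.** Section 11.5 states power 0.801 for 98 subjects and 3 repeated measures. Take the location with difference 0.36 cm and SD 0.77 cm: f is half the ratio of 0.36 to 0.77, which is 0.2338. With a within-subject correlation of 0.5 (assumed; not stated), the noncentrality is f² × 98 × 3, divided by one plus twice the correlation (here 2), which gives 8.03. With 1 and 96 degrees of freedom, power is 0.801. The stated figure therefore matches a between-subject group main effect. The group-by-time version gives 0.9995.

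**Error terms under equal correlation over time.** Write v_st for subject-by-visit variance, v_sl for subject-by-location variance and v_e for residual variance. With 4 occasions and 2 locations:

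- group-by-time needs error 2·v_st + v_e
- group-by-location needs error 4·v_sl + v_e
- a subject-intercept-only fit uses [3(2·v_st + v_e) + (4·v_sl + v_e) + 3·v_e]/7 = v_e + (6·v_st + 4·v_sl)/7

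The pooled term is right for group-by-time only if 14·v_st = 6·v_st + 4·v_sl, that is v_sl = 2·v_st. It is right for group-by-location only if 28·v_sl = 6·v_st + 4·v_sl, that is v_sl = v_st/4. Both hold only when both components are zero. This step needs no assumed variances.

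**Size, equal correlation.** Simulation under no effect: 49 per arm, 5,000 trials per setting, subject variance 0.25 and v_e 0.05. All variances (cm²) are assumptions.

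- v_sl zero and v_st 0.10: pooled error 0.136. Group-by-time needs 0.25 and rejects 23%; group-by-location needs 0.05 and rejects 0.2%.
- v_sl 0.10 and v_st 0.10: pooled error 0.193. Group-by-time needs 0.25 and rejects 10%; group-by-location needs 0.45 and rejects 21%.
- v_sl 0.20 and v_st 0.10: pooled error 0.250. Group-by-time needs 0.25 and rejects 5%; group-by-location needs 0.85 and rejects 30%.
- v_sl 0.20 and v_st zero: pooled error 0.164. Group-by-time needs 0.05 and rejects below 0.1%; group-by-location needs 0.85 and rejects 39%.

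Hand check of the last figure: 0.85 divided by the pooled error (0.1643 before rounding) is 5.17, and the chance that a standard normal exceeds 0.862 in absolute value (1.96 divided by the square root of 5.17) is 0.39.

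**Size, correlation decaying over time.** Occasions are placed at baseline, one day, 3 weeks and 8 weeks, with correlation exp(−gap/4 weeks) and subject variance 0.20. Baseline-to-last correlation is 0.135, baseline-to-next-day is 0.965, and the average of the six pairs is 0.415. A group contrast in change from baseline needs 2·v_st(1 − ρ) + v_e. The pooled error becomes v_e + [6·v_st(1 − r) + 4·v_sl]/7, where r is that average of 0.415.

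With v_st 0.10, v_sl zero and v_e 0.05, the pooled error is 0.100.

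- Baseline to last needs 0.223. The ratio is 2.23 and rejection is about 19%.
- Baseline to next day needs 0.057. The ratio is 0.57 and rejection is about 1%.

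Over v_st 0.05 to 0.20, baseline-to-last rejects about 8% to 22% when v_sl is 0.05 or less. It falls to about 2% when v_sl is 0.20 and v_st 0.05. Baseline-to-next-day rejects about 2% or less throughout. Group-by-time reaches 24%.

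**Alternatives in the same simulations.** A classical subject-by-time stratum holds about 5% under equal correlation. With decay it gives about 5.5% to 7.5%, and 8% to 11% for the baseline-to-last contrast. An unstructured visit covariance on location-averaged IRD holds 4.2% to 5.8% throughout. The group main effect from the subject-intercept model stays at 4.4% to 5.6%.

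**The case against.** The sentence on random effects sits in the sample-size justification and sorts factors by whether they generalise. It does not say subject is the only random term. The method named in 11.6 is a repeated-measures ANOVA, which in R can carry separate subject-by-time and subject-by-location strata. H01 and the model text name no group-by-time term. The power figure matches the group main effect, which is sound with complete balanced data. The simulated variances are not anchored in the documents.

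Most of this stands. A reader might infer that the primary test has an inflated false-positive rate. The documents do not support that: they do not commit to a subject-intercept-only fit, the direction can go either way, and the main effect is unaffected.

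What survives is that the only model components written down lead to the faulty fit. The plan intends contrasts after H01 is rejected. The charitable reading, a subject-by-time stratum, is adequate only if correlation is equal over time. Silence also leaves the error term to be chosen after the data are seen.

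**Conclusion.** The point holds as under-specification with a conditional consequence. That no single pooled error suits both interactions is algebra. The rejection rates rest on assumed variances, a 4-week decay, 49 completers per arm and no missing readings. Under equal correlation, a fit as listed is too liberal for group-by-time when v_sl is below 2·v_st, correct at equality and conservative above it. With decay it tends to over-reject late change unless v_sl is large, and it under-rejects next-day change, so a real early effect could be missed. Because nothing in the documents fixes the variances, no single error rate should be attached to this trial.

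**What to change.** In 11.5 and 11.6, replace the list of random and fixed effects with a stated model. The simplest version averages the two locations at each visit and fits group, occasion and group-by-occasion with an unstructured covariance over the four occasions. Use a small-sample degrees-of-freedom method such as Kenward-Roger. If location-specific effects matter, keep both locations, add a random subject-by-location term and retain the unstructured visit covariance. In either case, name the group-by-time contrast that answers the treatment question.

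While editing, reconcile the power statement (3 repeated measures, four locations) with the procedures (four occasions, two locations), and recompute power for the named contrast.

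The cost is a few lines of wording and standard R code. On averaged data the unstructured matrix has 4 × 5/2 = 10 parameters against 2 for a subject intercept plus residual, to be estimated from 98 planned completers. Averaging also gives up the group-by-location comparison.

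### Sections 11.5 and 11.6 do not say which term or contrast tests treatment, and leave the pre-treatment IRD already collected without a role; the 0.801 power belongs to one analysis that 11.6 does not define

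*Combined protocol and SAP*

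**What the plan says.** Section 11.1 defines the outcome: "The primary outcome measures are inter-rectus distances (IRD) taken 2 cm above and 2 cm below the umbilical ring". H01 is a single null: "there are no differences in IRD means between times, locations and treatment groups".

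Section 11.5 gives the model terms, "Fixed effects are treatment group, time of repeated measure, and IRD location", with subject as a random effect. The planning values are introduced as "The mean (SD) IRD at the four locations at 7 weeks postpartum": four means with SDs, and four minimal detectable changes (0.45, 0.47, 0.55 and 0.36 cm). The conclusion is that "98 subjects with 3 repeated measures will have a power of 0.801" at α = 0.05. The section does not say which of the four differences was used, what correlation was assumed, how many locations enter, or which three measures are meant.

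Section 11.6 says "Null hypothesis H01 will be tested by a mixed effects repeated measures analysis of variance (rANOVA) controlling for location and treatment group", and then "In the event the null hypothesis is rejected, contrasts will be used to investigate sub-group differences", with Holm correction. The contrasts are not listed.

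Section 10.1 schedules IRD four times: at Visit 1 before treatment, the next day ("Subjects will return to the clinic the day after visit 1 so that Research personnel can retrieve the microcurrent box"), at Visit 2 and at Visit 3. Section 12.5 requires an IRD of at least 2.5 cm for entry.

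**The concern.** H01 can be rejected because IRD changes over time in both arms, or because it differs above and below the umbilicus. Neither is evidence that the treatment works. The treatment conclusion has to come from a particular term or contrast, and the plan does not identify it. Three choices are open: which of the four measures enter, whether the pre-treatment one is a level of time or a covariate, and which contrast is primary. They could be settled after the data are seen.

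The choice also affects power. Randomised arms have an expected difference of zero before treatment. If that measure is kept as a time level, the group main effect averages the zero in with the post-treatment differences. Used as a covariate, the same measure removes variance instead.

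**Working it through.** **Inputs.** From Section 11.5: N = 98, three measures, α = 0.05, and the four difference/SD pairs 0.45/0.71, 0.47/0.59, 0.55/0.65 and 0.36/0.77 cm. From Section 12.5: entry at 2.5 cm. Assumed, because the documents do not give them: correlation ρ = 0.5 between any two measures, equal arms, one location, and the same difference at every post-treatment measure.

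**1. Reproduce 0.801.** For a between-groups main effect, f = (difference/SD)/2 and λ = f²N/v, where v = (1 + (m−1)ρ)/m is the variance of a subject's mean over m measures in SD² units. The F test has 1 and N−2 df.

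- For 0.36/0.77: f = 0.4675/2 = 0.2338 and f²N = 5.355. With m = 3, v = 2/3 and λ = 8.03, so power = **0.801**. N = 97 gives 0.797.
- The other three pairs give 0.967, 0.998 and 0.999. With 0.36/0.77, m = 2 gives 0.754 and m = 4 gives 0.826.

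So 0.36/0.77 is inferred: it is the only listed pair that returns the stated figure under this method. The calculation puts the full 0.36 cm at all three measures, which fits the next-day, Visit 2 and Visit 3 measures.

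**2. Baseline kept as a time level, unrestricted baseline.**

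- One of three: the difference shrinks by 2/3, so λ = 5.355 × (4/9)/0.667 = 3.57 and power = 0.46.
- One of four: it shrinks by 3/4 and v = 2.5/4 = 0.625, so λ = 5.355 × (9/16)/0.625 = 4.82 and power = 0.58.

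**3. Baseline as covariate, unrestricted baseline.** With baseline-to-post correlation r, v = 2/3 − r² and the df are 1 and 95.

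| r | v | λ | Power |
|---|---|---|---|
| 0.5 | 0.417 | 12.85 | 0.94 |
| 0.3 | 0.577 | 9.29 | 0.85 |
| 0 | 0.667 | 8.03 | 0.80 |

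**4. Carry the entry criterion through.** Suppose IRD before selection is normal with the planning values 1.30 (0.77) cm and only women at or above 2.5 cm enter.

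- Cut-off: a = (2.5 − 1.30)/0.77 = 1.558. With h = φ(a)/(1 − Φ(a)) = 1.989, the share of baseline variance kept is k = 1 + ah − h² = 0.145. The baseline SD is then 0.77 × √0.145 = 0.29 cm.
- Baseline-to-post covariance: ρk = 0.072. Post-treatment variance: 1 − ρ²(1 − k) = 0.786. Post-to-post covariance: ρ − ρ²(1 − k) = 0.286.
- Baseline-to-post correlation in enrolled women: 0.072/√(0.145 × 0.786) = 0.21.

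| Analysis, ρ = 0.5 before selection | No restriction on baseline | Truncated at 2.5 cm |
|---|---|---|
| Three post-treatment measures, unadjusted | 0.80 | 0.93 (v = 0.453, λ = 11.8) |
| Group term, baseline one of three levels | 0.46 | 0.81 (v = 0.287, λ = 8.3) |
| Group term, baseline one of four levels | 0.58 | 0.89 (v = 0.291, λ = 10.4) |
| Three post-treatment measures, baseline as covariate | 0.94 | 0.94 (v = 0.417, λ = 12.9) |

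Adjusted power is the same in both columns because selection on baseline leaves the variance around the baseline regression unchanged. The gain from the covariate is 0.14 in the first column and about 0.02 in the second.

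**The case against.** The plan does point to a test of treatment. Section 11.5 powers for differences between the arms and lists group as a fixed effect, H01 includes groups, and 11.6 names the model family. A colleague would probably run the group main effect over the three post-treatment measures, and on that reading 0.801 stands at correlation 0.5. It would be over-literal to conclude from the wording about controlling for treatment group that treatment is only a nuisance term. This stands: what is missing is a stated contrast, not an analysis.

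Under randomisation the unadjusted post-treatment comparison is valid, so leaving out the covariate loses efficiency and introduces no bias. That also stands.

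A reader might go further and infer that the trial's real power is about 0.46 to 0.58. The documents do not support this. No section says that the pre-treatment measure is averaged into the group term. Those figures also give baseline its full SD of 0.77 cm, although entry is restricted to 2.5 cm or more; with that restriction carried through the same normal model they become 0.81 and 0.89. They rest as well on the smallest of four listed differences, and 11.5 selects none of them.

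**Conclusion.** The gap in specification holds. Sections 11.5 and 11.6 leave open the term or contrast that tests treatment, the three measures meant, and the role of the pre-treatment IRD. The 0.801 itself is sound for an unadjusted, single-location group main effect at 0.36 cm, SD 0.77 and correlation 0.5, with all three measures after treatment.

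Keeping baseline as a time level would lower power, and the covariate would raise or maintain it. The size of either effect depends on how strongly baseline predicts later IRD in enrolled women, which the documents do not give. A reader might take the step from 0.80 to 0.94 as the expected gain from adjustment. That is not supported: with no restriction on baseline, power goes from 0.80 to 0.85 at a baseline-to-post correlation of 0.3 and to 0.94 at 0.5, but under truncation at 2.5 cm only from about 0.93 to 0.94.

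The truncated figures assume normality, that the planning distribution describes women before selection, and that the location analysed is the one used for eligibility. They show how far the size can move and are not a forecast. The recommendation does not depend on them, because the covariate costs essentially nothing even if uncorrelated with later IRD (0.80 with or without it). This should be fixed, but it does not invalidate the sample size.

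**What to change.** **Section 11.6.** Define the primary treatment test as the arm difference in IRD over the three post-treatment measures (next day, Visit 2, Visit 3), with pre-treatment IRD at the same location as covariate, fixed effects for group, time and location, and subject as a random effect. Report the arm difference in cm and as a percentage of the sham mean, with a 95% confidence interval, beside the 30% target in Section 11.5.

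**Section 11.5.** State that 0.801 is the power of the unadjusted, single-location group main effect at 0.36 cm, SD 0.77 and correlation 0.5, once the study team has confirmed these inferred inputs, and that the three measures are the post-treatment ones. Say that baseline adjustment is expected to maintain or raise power, by an amount that depends on the baseline-to-post correlation in enrolled women. Do not state a fixed gain.

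**Cost.** Rewording of two sections, to be done before the allocation is revealed for analysis. No extra participants, visits or measurements are needed, because the pre-treatment IRD is already taken at Visit 1.
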